9.5. Pharmacokinetics

9.5.1. Open-label PK Lead-in (Study Period 2)

Blood samples will be collected during the Open-label PK Lead-in period using a commercially available microsampling device (see Schedule of Activities in Section 2). These blood samples will be used to determine the concentrations of baricitinib using a validated bioanalytical method. The timing will be as follows:

- At Visit 2 (Week 0/Day 1), patients will take their first dose of IP in the clinic, and PK samples will be collected 15 minutes and 1 hour postdose.
- On Day 2 and thereafter: patients will take their IP once daily at home. Patients should be instructed to take their dose at approximately the same time each day.
- On Day 4, patients will take their IP at home, and PK samples will be collected at 2 hours and 4 hours postdose. If PK samples are not collected on Day 4, they may be collected on the following days up to and including the date of Visit 3 (Week 1).

- On Day 11, a PK sample will be collected BEFORE the IP is taken. Immediately after the PK sample is collected, the patient will take the IP, and PK samples will be collected at 30 minutes and 6 hours postdose. If PK samples are not collected on Day 11, they may be collected on the following days up to and including the date of Visit 4 (Week 2). All PK samples must be completed before the patient leaves the clinical site at Visit 4.

One patient in the older age group may be selected to provide 1 venous blood sample to assess concordance between venous blood samples and microsamples. During Study Period 2, the actual date and 24-hour clock time of the PK sample collection, and the date and time of the last 2 doses of IP will be recorded. For samples drawn on Day 4 and 11, the 2 previous doses should be the dose given on the day of the PK sample collection and the dose given the previous day.

9.5.2. Double-blind Treatment Period (Study Period 3)

A venous blood sample will be drawn at the times indicated in the Schedule of Activities (Section 2) (Weeks 0 [first dose, 2 samples], 4, 8, 12, and 16). These blood samples will be used to determine the plasma concentrations of baricitinib using a validated bioanalytical method.

The timing will be as follows:

- At Visit 2 (Week 0), patients will take their IP in the clinic, and PK samples will be drawn 15 minutes and 1 hour postdose. NOTE: At Visit 2, all other laboratory samples (i.e., all non-PK samples) will be obtained prior to the first dose of IP in order to ensure accurate baseline data are collected.
- At Visit 5 (Week 4), patients will be asked to take their IP at home prior to visiting the clinic. The clinic visit should be scheduled so that the blood sample collected during this visit is drawn 2 to 4 hours after the dose is taken at home.
- For Visit 6 (Week 8) and Visit 7 (Week 12) patients will be asked to not take their IP before visiting the clinic, and a blood sample will be collected at any time predose on the day of the clinic visits. If the patient has taken the oral dose prior to the visit, the sample may be drawn anytime postdose, and the inability to collect a predose sample will not be considered a protocol violation.
- At Visit 8 (Week 16), patients will be asked to take their IP at home prior to visiting the clinic. The clinic visit should be scheduled so that the blood sample collected during this visit is drawn 4 to 6 hours after the oral dose is taken at home.
- For the ETV, a sample may be drawn anytime if the last dose of IP was taken within the last 48 hours.

For visits where PK samples will be collected, the actual date and 24-hour clock time of sample collection, and the date and time of the last 2 doses prior to the sample being drawn, should be recorded. At Visit 5 (Week 4) and Visit 8 (Week 16), these 2 doses should be the dose given the morning of the day of sample collection and the dose given the previous day. At Visit 6 (Week 8) and Visit 7 (Week 12), the 2 previous doses should be the dose taken yesterday and the dose taken the day before that.

This sampling schedule should be followed as closely as possible; however, failure to take PK samples at these specified times will not be considered a protocol violation. If the patient fails to follow the directions for a particular visit, the sample should still be collected at that visit, and the date and 24-hour clock time of sample collection and the date and time of the 2 doses prior to the sample being drawn should be recorded.

Only samples from patients receiving baricitinib will be assayed; samples from patients receiving placebo will not be assayed. Pharmacokinetic samples will be kept in storage at a laboratory facility designated by the Sponsor. Pharmacokinetic samples may also be assayed for additional exploratory analyses. Pharmacokinetic results will not be provided to investigative sites until the completion of the study or to the blinded study team until the study has been unblinded.

Bioanalytical samples collected to measure IP concentration will be retained for a maximum of 1 year following last patient visit for the study.

9.6. Pharmacodynamics

Refer to Section 10.3.6.

9.6.1. Whole Blood Samples for Pharmacogenetic Research

A whole blood sample will be collected for pharmacogenetic analysis as specified in the Schedule of Activities (Section 2) where local regulations allow.

Samples will not be used to conduct unspecified disease or population genetic research either now or in the future. Samples will be used to investigate variable response to baricitinib and to investigate genetic variants thought to play a role in AD. Assessment of variable response may include evaluation of AEs or differences in efficacy.

All samples will be coded with the patient number. These samples and any data generated can be linked back to the patient only by the investigator site personnel.

Samples will be retained at a facility selected by Lilly or its designee for a maximum of 15 years after the last patient visit for the study, or for a shorter period if local regulations and/or ethical review boards (ERBs)/investigational review boards (IRBs) impose shorter time limits. This retention period enables use of new technologies, response to regulatory questions, and investigation of variable response that may not be observed until later in the development of baricitinib or after baricitinib becomes commercially available.

Molecular technologies are expected to improve during the 15-year storage period and therefore cannot be specifically named. However, existing approaches include whole genome or exome sequencing, genome wide association studies, and candidate gene studies. Regardless of technology utilized genotyping data generated will be used only for the specific research scope described in this section.

9.7. Biomarkers

Biomarker research is performed to address questions of relevance to drug disposition, target engagement, pharmacodynamics [PD], mechanism of action, variability of patient response

(including safety), and clinical outcome. Sample collection is incorporated into clinical studies to enable examination of these questions through measurement of biomolecules including DNA, RNA, proteins, lipids, and other cellular elements.

Blood samples for biomarker research will be collected at the times specified in the Schedule of Activities (Section 2) where local regulations allow.

Samples will be used for research on the drug target, disease process, variable response to baricitinib, pathways associated with AD, mechanism of action of baricitinib, and/or research method or in validating diagnostic tools or assay(s) related to AD.

All samples will be coded with the patient number. These samples and any data generated can be linked back to the patient only by the investigator site personnel.

Samples will be retained at a facility selected by Lilly or its designee for a maximum 15 years after the last patient visit for the study, or for a shorter period if local regulations and ERBs impose shorter time limits. This retention period enables use of new technologies, response to regulatory questions, and investigation of variable response that may not be observed until later in the development of baricitinib or after baricitinib becomes commercially available.

9.8. Medical Resource Utilization and Health Economics

The EQ-5D-Y is being utilized in this study to collect data for input into economic models. See Section 9.1.4.11 for instrument description.

10. Statistical Considerations

10.1. Sample Size Determination

Approximately 25 patients will be enrolled into the Open-label PK Lead-in (Study Period 2) and may continue on open-label treatment during the long-term extension (Study Period 4). Data from patients participating in the PK lead-in will be analyzed separately from patients randomized into the Double-blind treatment (Study Period 3).

Study JAIP will aim to enroll at least 440 patients 2 to <18 years of age into the Double-blind Treatment period (Study Period 3), which includes at least 320 older pediatric patients (10 to <18 years) and at least 120 younger pediatric patients (2 to <10 years). The proposed sample size (N=440) will ensure a >95% power to detect any difference between the baricitinib high dose and placebo treatment groups or the baricitinib medium dose and placebo treatment groups, each using a 2-sided alpha of 0.05, assuming a 10% placebo, 25% medium dose, and 30% high dose response rate for the primary endpoint using a chi-squared test. The assumptions are based on what was observed in the Phase 2 study (JAHG). The proposed end point of IGA 0 or 1 represents patients whose AD is clear or almost clear from a baseline of moderate or severe disease. The anticipated effect size represents 3 times more patients achieving this benefit compared to placebo which, in discussion with therapeutic experts, is of a magnitude that is considered to be clinically relevant.

Furthermore, in older pediatric patients the sample size of 320 is sufficient to detect that the baricitinib high or medium dose is superior to placebo at least 80% of the time. Similarly, in the younger pediatric patients, the planned sample size of 120 patients has > 80% simulated power using the Bayesian approach described in Section 10.3.7.3 and in the Study JAIP SAP to detect any difference between the baricitinib high dose or medium dose and placebo treatment groups with a probability threshold of 0.95.

The primary analysis will be conducted using a logistic regression analysis with region, disease severity (IGA), age, treatment group, and treatment group-by-age interaction in the model. The p-value and 95% confidence interval (CI) for the odds ratio from the logistic regression model are used for primary statistical inference. The primary analysis will include data from the entire study population 2 to <18 years old, and a frequentist approach will be used for the analysis. However, in the event that the older subgroup of patients (10 to <18 years old) completes the Double-blind Treatment period (Study Period 3) more than 6 months earlier than anticipated for the younger subgroup of patients (2 to <10 years old), each age subgroup is adequately powered and can be individually unblinded and analyzed according to a pre-planned analysis approach as described in Section 10.3.8 below. This is to ensure that potential delay in completing the enrollment of the younger patients will not delay analysis and submission of the data from the older patients.

Sample size estimates were calculated using nQuery® Advisor 7.0 for the older subgroup of patients, and power estimates were obtained from R 3.5.0 and JAGS 4.2.0 for the younger subgroup of patients.

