The study will be carried out using an intent-to-treat population defined as all randomized patients for the efficacy analyses. The primary efficacy measure is the binary outcome of response defined as an IGA score of 0 or 1 (clear or almost clear) with a ≥ 2 -point improvement at Week 16. Given the sample size and a non-responder imputation (NRI) method for missing data, the current sample size (N=440 with 1:1:1:1 randomization) will ensure a >95% power to detect any difference between the baricitinib high dose and placebo treatment groups or the baricitinib medium dose and placebo treatment groups, each using a 2-sided alpha of 0.05, assuming a 10% placebo, 25% medium dose, and 30% high dose response rate for the primary endpoint. Patients who are rescued or discontinue treatment will be considered non-responders. Treatment group comparisons for binary efficacy response measures will be analyzed using a logistic regression. The primary analysis will be conducted using a logistic regression analysis with region, disease severity (IGA), age, treatment group, and treatment group-by-age interaction in the model. Other secondary measures of efficacy that are continuous will be analyzed using mixed-model repeated measures (MMRM) methodology. Placebo multiple imputation and last observation carried forward methods will also be used for analysis of continuous endpoints. Population PK and PK/PD analyses based on data from the Double-blind Treatment period will be used to characterize the PK of baricitinib and to explore relationships between baricitinib exposure and efficacy and/or safety endpoints. In the case of slower enrollment for the younger pediatric subgroup (i.e., the older pediatric subgroup completes the double-blind treatment period more than 6 months earlier than the anticipated completion date for the younger subgroup of pediatric patients), the older pediatric subgroup may be analyzed first according to a pre-planned analytical approach to support timely regulatory submission.

Safety analyses will be conducted using the safety population defined as all randomized patients who received at least 1 dose of investigational product (IP) and who did not discontinue from the study for the reason 'Lost to Follow-up' at the first postbaseline visit.

2. Schedule of Activities

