10.3.7.3. Subgroup Analyses

To assess whether the treatment effect is similar across subgroups for the primary efficacy outcome, a logistic model will be used and will include treatment, stratification variables, the subgroup variable (e.g., age) and the subgroup by treatment interaction. If the interaction is statistically significant at $\alpha=0.10$, the nature of the interaction will be explored, that is, within each subgroup the treatment effect will be estimated. Similarly, for the continuous variable of EASI, the MMRM analysis will include additional variables for subgroup and the subgroup by treatment interaction.

Subgroups to be evaluated will include baseline disease severity, sex, age (<10 years or ≥ 10 years), race, prior therapy (intolerance or inadequate response to TCS/TCNI), other atopic conditions (e.g., food allergies, asthma, allergic rhinitis/rhinoconjunctivitis). Further definitions for the levels of the subgroup variables, the analysis methodology, and any additional subgroup analyses will be defined in the SAP. Because this study is not powered for subgroup analyses, all subgroup analyses (with the exception of age cohorts, which are adequately powered) will be treated as exploratory.

In the subgroup of older pediatric patients (10 to <18 years old), a frequentist approach will be used.

Younger Pediatric Patients (2 to <10 years old)

In the subgroup of younger pediatric patients (2 to <10 years old), a hierarchical Bayesian analysis will be conducted using a logistic regression analysis as described above. This logistic regression will also include covariate adjustments for disease severity (IGA) and treatment group in the model. The posterior probability and 95% credible interval (CrI) for the difference in proportion from the logistic regression model are used for primary statistical inference. Details of the Bayesian approach are described in the SAP.

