10.3.8. Interim Analyses

No interim analyses are planned for this study. The analysis of Study Period 3 data is considered to be the primary analysis. If an unplanned interim analysis is deemed necessary, the appropriate Lilly medical director, or designee, will be consulted to determine whether it is necessary to amend the protocol. Additional analyses in order to support regulatory submission may be required after patients have completed the primary endpoint during Study Period 3, and these additional analyses will be specified in the SAP.

In the event that the older subgroup of patients (10 to <18 years old) completes the Double-blind Treatment period (Study Period 3) more than 6 months earlier than the anticipated completion date for the younger subgroup of patients (2 to <10 years old), each age subgroup is adequately powered and can be individually unblinded and analyzed according to a pre-planned analytical approach. In this pre-planned approach, the older subgroup of patients will be locked and analyzed (using a frequentist approach) after all patients in the subgroup have completed or discontinued from Study Period 3, and this analysis will be considered the primary analysis for the older subgroup. Subsequently, after all patients in the younger subgroup have completed or discontinued from Study Period 3, the data from the younger subgroup will be locked and analyzed (using a Bayesian approach), and this analysis will be considered the primary analysis for the younger age subgroup. The database lock and analysis of the data from the older subgroup of patients will not be considered an interim analysis and no alpha will be spent because the analysis of each age subgroup will be conducted independently and will be considered the primary analysis for the age group. In this situation, the combined analysis of the entire study population (2 to <18 years old) will be considered a secondary analysis. Further details of this pre-planned analytical approach will be included in the study JAIP SAP.

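### Read per dose, the >95% power claimed for N=440 holds for the high dose (about 96%) but not for the medium dose (about 84–85%)

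*Protocol*

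**What the plan says.** Section 10.1 claims that 440 patients "will ensure a >95% power to detect any difference between the baricitinib high dose and placebo treatment groups or the baricitinib medium dose" (likewise compared with placebo). The conditions it attaches to the primary endpoint are these: "each using a 2-sided alpha of 0.05, assuming a 10% placebo, 25% medium dose, and 30% high dose response rate". It names a chi-squared test. The Synopsis makes the same claim: "the current sample size (N=440 with 1:1:1:1 randomization) will ensure a >95% power to detect any difference between the baricitinib high dose and placebo", again extended to the medium dose. Both places give 1:1:1:1 allocation or its result, 110 patients per arm, as does Section 5.1.

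Section 10.1 supports the clinical relevance of the effect with this sentence: "The anticipated effect size represents 3 times more patients achieving this benefit compared to placebo".

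For the older cohort it adds a claim of 80% power or more, without response rates or alpha: "in older pediatric patients the sample size of 320 is sufficient to detect that the baricitinib high or medium dose is superior to placebo". Three later statements rest on power within the age cohorts. Section 10.1 says "each age subgroup is adequately powered and can be individually unblinded and analyzed according to a pre-planned analysis approach", Section 10.3.8 repeats "each age subgroup is adequately powered and can be individually unblinded and analyzed", and Section 10.3.7.3 says "all subgroup analyses (with the exception of age cohorts, which are adequately powered) will be treated as exploratory".

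**The concern.** The medium dose is assumed to beat placebo by 15 points and the high dose by 20. Two effects that far apart, tested in arms of equal size at the same alpha, will not have the same power, yet one figure is given for both. The relevance argument also fits only one of them: 30/10 = 3.0 for the high dose, 25/10 = 2.5 for the medium dose. This suggests, without proving it, that the high-dose power was carried over to both doses.

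The primary objective in Section 4 is superiority of each dose over placebo, so the medium-dose figure matters in its own right. A reader who takes the claim at face value puts the chance of missing the assumed medium-dose effect below 1 in 20, and would read a non-significant medium-dose result as stronger evidence against that dose than it is. If the older cohort finishes more than 6 months early and is analysed alone, the statement that each cohort is adequately powered carries the same weight there.

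**Working it through.** **Inputs for N=440.** All are stated in Section 10.1, with arm size also in Section 5.1: n = 440/4 = 110 per arm; p = 0.10 placebo, 0.25 medium, 0.30 high; 2-sided alpha 0.05; chi-squared test. No inflation for dropout applies, because missing data and rescue count as non-response.

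**Formula (normal approximation, pooled variance under the null).** With p̄ = (p₁+p₂)/2,

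power = Φ{ [ (p₂−p₁) − 1.96·√(2p̄(1−p̄)/n) ] / √[ (p₁(1−p₁)+p₂(1−p₂))/n ] }.

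**High dose, which reproduces the stated figure.** p̄ = 0.20; null SE = √(0.32/110) = 0.0539; alternative SE = √(0.30/110) = 0.0522.
(0.20 − 1.96×0.0539)/0.0522 ≈ 1.81, so power = **96.4%**.

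**Medium dose.** p̄ = 0.175; null SE = √(0.28875/110) = 0.0512; alternative SE = √(0.2775/110) = 0.0502.
(0.15 − 1.96×0.0512)/0.0502 ≈ 0.99, so power = **83.8%**.

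**Other methods, 110 per arm.** The exact figures sum binomial probabilities over all outcomes where the test rejects in favour of baricitinib.

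| Method | High | Medium |
|---|---|---|
| Pooled normal | 96.4% | 83.8% |
| Unpooled normal | 96.9% | 84.8% |
| Exact, uncorrected chi-squared | 96.9% | 84.9% |
| Exact, continuity-corrected or Fisher | 95.6% | 80.4% |
| One-sided 0.05, pooled normal | 98.3% | 90.5% |

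The high dose exceeds 95% in every row; the medium dose does so in none. For the medium dose to reach 95% with 110 per arm, its true rate would have to be about 29% (28.7% exact), close to the assumed high-dose rate. At 25% it would need about 164 per arm.

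**Joint readings (exact, shared placebo arm).** Let π_H(x) and π_M(x) be the chances of rejection for each dose given x placebo responders.
- At least one dose: Σ P(x)[1 − (1−π_H(x))(1−π_M(x))] = **98.4%**
- Both doses: Σ P(x)π_H(x)π_M(x) = **83.4%**

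**Older cohort.** The rates and alpha are not stated. Assume the same 10/25/30%, alpha 0.05 and 320/4 = 80 per arm.
- High: (0.20 − 1.96×√(0.32/80))/√(0.30/80) ≈ 1.24, so 89.3% (exact 90.3%)
- Medium: (0.15 − 1.96×√(0.28875/80))/√(0.2775/80) ≈ 0.55, so 70.8% (exact 71.6%)
- At least one dose (exact): 94.1%

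Range for the older medium dose (normal approximation):

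| Placebo rate | Medium rate | Power |
|---|---|---|
| 10% | 23 / 25 / 27 / 28% | 60 / 71 / 80 / 83% |
| 8 / 9 / 10 / 12% | 25% | 83 / 77 / 71 / 56% |

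So 80% for the medium dose needs a medium rate of about 27% or more, or a placebo rate of about 8.6% or less.

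**The case against.** The strongest reply is that the wording is disjunctive throughout: the claim covers the high *or* the medium dose. If that means success on at least one dose, both figures hold: 98.4% against >95% for N=440 and, with the same rates, 94.1% against at least 80% for the older cohort. Splitting alpha does not overturn this. At 0.025 and 0.0167 per dose the at-least-one-dose power is 96.7% and 95.3% for N=440, and 89.3% and 85.5% for the older cohort (illustrative, since the allocation is left to the SAP). A reading that makes the text coherent deserves weight. But the protocol never says at least one dose, it gives a separate rate for each dose and an alpha for *each* comparison, and its objective is superiority of each dose. The per-dose reading is the more natural one.

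Four narrower points stand in part.
- The older-cohort shortfall rests on assumed rates, and small shifts in them restore 80%. Section 10.1 mentions a software calculation for that cohort but not its inputs. What is shown there is missing inputs, not an arithmetic error.
- The primary analysis is a covariate-adjusted logistic regression within a graphical multiplicity procedure. The 84–85% checks the chi-squared claim as printed and is not the miss rate of that analysis. A split alpha would lower it; at 0.025 the medium dose has about 76% (normal approximation).
- The threefold sentence is correct for the high dose and does not expressly claim to cover the medium dose.
- Medium-dose power at N=440 remains above the 80% the protocol accepts for its age cohorts.

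**Conclusion.** The concern holds. On the more natural, per-comparison reading, the >95% figure in Section 10.1 and the Synopsis is right for the high dose and overstates the medium dose by 10 to 11 points. This uses only stated inputs and no standard variant of the test closes the gap. Under the stated test, the chance of missing the assumed medium-dose effect is about 1 in 6, not under 1 in 20. On the at-least-one-dose reading the number is right, but the sentence does not convey it, so it needs repair either way.

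For the older cohort the conclusion is conditional. If the N=440 rates and alpha apply, the medium dose has about 71–72% power, a miss chance of about 3 in 10, and the statement of adequate power is supported for the high dose only.

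This should be fixed, but it does not threaten the design.

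**What to change.** - **Synopsis and Section 10.1:** give power by dose for N=440, about 96% high and 84% medium, for the chi-squared test at 2-sided 0.05.
- **Section 10.1, older cohort:** state the assumed rates and alpha and give power by dose. If the 10/25/30% rates and 0.05 apply, that is about 89% high and 71% medium.
- **Sections 10.1, 10.3.7.3 and 10.3.8:** qualify the statement of adequate power by dose, in line with the inputs given.
- **If at-least-one-dose power was meant:** say so and report it as a separate, labelled figure.
- **Threefold sentence:** tie it to the high dose, or add the 2.5-fold medium-dose effect.
- **Split-alpha figures:** label any as illustrative until the SAP's allocation is applied.

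The cost is wording and restated figures. Sample size, design and analysis do not change.
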